Exposure-response (E-R) relationships for efficacy and toxicity were characterized with data obtained from 3 Phase II studies in subjects with advanced melanoma (CA184007, CA184008, and CA184022). E-R relationship was assessed for 2 measures of efficacy: best overall response (BOR) defined by mWHO criteria, and immune-related clinical activity (irCA). ir-Clinical Activity includes subjects with ir complete response irCR, or ir partial response (irPR), or late response (irCR or irPR or ir stable disease (irSD) after tumor progression), or subjects who achieved irSD of  $\geq 25\%$  reduction in tumor burden from baseline. The safety endpoint employed was the incidence of immune-related adverse events (irAEs). The probability of BOR and irCA increased with increasing minimum plasma concentration (Cmin) of ipilimumab at steady-state (Cmin,ss) over the range of exposures achieved by ipilimumab doses ranging from 0.3 to 10 mg/kg. Likewise, the probability of experiencing Grade  $\geq 2$  and Grade  $\geq 3$  irAEs also increased with Cmin,ss of ipilimumab. The majority of these events were medically manageable and resolved within days to weeks following cessation of ipilimumab or treatment with corticosteroids or other anti-inflammatory agents.

Recent data (in press; cross study analysis from CA184007, CA184008, CA184022) has been provided by the BMS Ipilimumab Team. In cell based competition assays in vitro, a Cmin,ss (minimum plasma concentration at steady-state) of 20mcg/ml of ipilimumab has been shown to maximally block CTLA-4 binding to B7-1 and B7-2. Analysis of PK data from patients treated with ipilimumab at 0.3 mg/kg (N=47), 3 mg/kg (N=60) and 10 mg/kg (N=311), showed that the target Cmin,ss target threshold of 20 mcg/ml was exceeded in 0% subjects receiving 0.3 mg/kg, 30% subjects receiving 3 mg/kg and 95% subjects receiving 10 mg/kg. In addition the 10 mg/kg dose level has been shown to be more biologically active than 3 or 0.3 mg/kg. The mean absolute lymphocyte count (ALC) increases proportionally with the ipilimumab dose with an ALC slope that is correlated with ipilimumab dose ( $p < 0.0001$ ) and with clinical benefit (CR, PR, SD  $\geq 6$  months) ( $p = 0.0013$ ).

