7. Submit to ECOG-ACRIN Immunologic Monitoring and Cellular Products Laboratory.
8. Submit from patients who have consented to have tissue submitted for research.
9. Mandatory submission for central review.
10. [Deleted in Addendum #5]
11. [Deleted in Addendum #5]
- Rev. 8/12, 9/14 12. On the day of the scheduled administration of the second dose of ipilimumab (day 22 +/- 3 days) and **before administering the second dose** of ipilimumab on Arms A, C, D, and F (up to one week prior to the scheduled administration of the second dose is acceptable if not possible on the same day). On the day of initiation of maintenance subcutaneous IFN (day 29 +/- 3days) on Arm B or E (up to one week prior to initiation of maintenance subcutaneous IFN is acceptable if not possible on the same day). If the study treatment was delayed or discontinued for that day due to adverse events the blood specimen should still be collected.

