**XIX.3 Choice of Trial**

These correlatives will be utilizing banked biospecimens (pre-treatment and 3-4 weeks post initiation of treatment) in subjects previously consenting to the future use of their banked biospecimens for research purposes. E1609 trial that is testing adjuvant ipilimumab (at high dose and standard dose) versus IFN $\alpha$  in patients with operable stage IIIB/C and M1a/b melanoma who are at high risk for recurrence and death. The large sample size (N ~ 1600) and diverse banked biorepository for E1609 make it an ideal platform through which to evaluate these interrelated markers for their prognostic and immunotherapeutic predictive value with regard to ipilimumab in reference to IFN $\alpha$ , as assessed individually and in combination based on the common systems biology. E1609 will allow the development of a therapeutic predictive model that links circulating markers of the pro-inflammatory response and immunosuppression with markers in the tumor microenvironment. This trial also allows the evaluation of potentially toxicity-predictive biomarkers, the most devastating of which has been autoimmune colitis.

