**XIX.8 Statistical Design**

**Endpoints (outcomes)**

The clinical endpoints are relapse free survival (RFS) and overall survival (OS). RFS is defined as the time from study entry to relapse or death, whichever happens first. OS is defined as the time from study entry to death.

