### Searching for predictive biomarkers

Based on our and others studies, we have defined a pool of candidate prognostic biomarkers. We expect that some of these markers are also predictive. Thus, we would consider these markers as our top tier candidate predictive markers. First, we will follow the recommendation by Janes et al, and use the marker-by-treatment predictive curves using 1-year PFS (or 1-year OS) as the "response rates" to evaluate the interaction between the marker and the treatment. Only the markers with a qualitative interaction with the treatment will be further investigated, since they are the only markers that could guide the choice of treatments. We will dichotomize marker around the point where the two predictive curves cross. To test the interaction between the marker and treatment, we will fit the Cox proportional hazard model of the following form:  $\lambda(t) = \lambda_0(t) \times \exp\{\beta_1 Md + \beta_2 T + \beta_3 T * Md + \sum \beta_i \text{Covariates}\}$ , where Md denotes dichotomized marker value, T denotes treatment (HDI/HIP/LIP), the function  $\lambda(t)$  represents the event rate at time t, and  $\lambda_0(t)$  represents the corresponding baseline event rate. Likelihood ratio test will be used to test the null hypothesis of  $\beta_3=0$ . To adjust for the multiple testing, the Benjamini and Hochberg's (BH) method will be used to control the false-discovery rate (FDR) at 5%. We may also consider the risk score from the prognostic models developed above as a continuous marker and analyze them in the same way as described above. Markers (and risk scores) that show a significant qualitative interaction with the treatment effect will be further ordered by the estimated 1-year RFS (or OS) rate under the marker-policy. The top few (<5) predictive biomarkers may be validated in the

validation set. Given the lack of preliminary data on predictive biomarkers, if our search among the top tier markers failed, we will consider a genomic scan of gene expression to search for potential predictive biomarkers using the same strategy described above in the training dataset.

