#### **Detailed Analysis Plan for the Primary Objective**

**Association of individual markers with clinical outcome.** The association of each marker at each time point with the RFS will be assessed by Cox proportional hazard regression (CoxPH), adjusted for treatment arm and known prognostic factors such as age, sex, Breslow thickness, recurrent disease at study entry, ulceration of the primary tumor, lymph-node status, number of positive lymph nodes, completion of lymph node dissection prior to treatment, microscopic extranodal extension, and mitotic rate. Schematically, we will fit models of the following form:  $\lambda(t) = \lambda_0(t) \times \exp\{\beta_1 M + \beta_2 T + \beta_i \text{Covariates}\}$ , where M denotes marker value (e.g., the absolute lymphocyte count, ALC), T denotes treatment (HDI/HIP/LIP), the function  $\lambda(t)$  represents the relapse rate at time t, and  $\lambda_0(t)$  represents the corresponding baseline relapse rate. Because some long-term cures have been observed in patients with stages IIB – III melanoma treated with HDI and ipilimumab, we will also perform exploratory analyses using a cure-rate model for RFS as a supplement to the CoxPH regression analyses proposed above. The cure-rate model assumes that the population being studied is a mixture of two subpopulations: one of which is cured (proportion  $\pi$  of the study population), and the other of which is not (proportion  $1 - \pi$  of the study population). We represent the survival function in this latter subpopulation by  $S_2(t)$ . The survival function  $S(t)$  for the entire study population is a simple mixture of the two:  $S(t) = \pi + (1 - \pi)S_2(t)$ . Similar approaches will be used for the statistical analysis of OS data. To adjust for the multiple testing, the Benjamini and Hochberg’s (BH) method will be used to control the false-discovery rate (FDR) at 5%. ***Note that this marker-by-marker analysis is not intended for the feature selection of the multi-marker model building***

***described in the next section. This analysis is to test the marginal association of each candidate marker. The feature selection step for the model building is included in the cross-validation loop to avoid over-fitting.***

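### Appendix XIX lets week 3-4 circulating markers, or a risk score built on them, enter the marker-by-treatment test and set a treatment-selection cut-point, although treatment has already changed them

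*Combined protocol and SAP*

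**What the plan says.** **Specimens.** Section XIX.3 says that the correlative work uses banked material taken "pre-treatment and 3-4 weeks post initiation of treatment". Section 7.4 fixes the second draw. On the ipilimumab arms it is "On the day of the scheduled administration of the second dose of ipilimumab (day 22 +/- 3 days". For interferon it is "On the day of initiation of maintenance subcutaneous IFN (day 29 +/- 3days) on Arm B or E".

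**Outcome and model.** In XIX.8, "RFS is defined as the time from study entry to relapse or death, whichever happens first". In XIX.9 the marker is a fixed covariate: "The association of each marker at each time point with the RFS will be assessed by Cox proportional hazard regression (CoxPH". No landmark, delayed entry or rule for patients without the on-treatment sample is given.

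**Route to the predictive test.** Hypothesis 1 in XIX.1 allows the signature to be built from baseline values, early on-treatment values or both. Secondary objective (a) in XIX.2 tests that signature for predictive value. The section on searching for predictive biomarkers adds: "We may also consider the risk score from the prognostic models developed above as a continuous marker". It keeps only markers with a qualitative interaction, because only those could steer the choice between treatments, and it dichotomizes each marker where the two predictiveness curves cross. None of these passages limits the test to pre-treatment values.

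**Balance.** The power calculation for predictive modeling takes the marker distribution to be the same in both arms because the trial is randomized.

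**The concern.** A marker that selects treatment must be known before treatment starts, and its distribution must not depend on arm. A week 3-4 value meets neither condition. If treatment changes the marker, marker-low patients on ipilimumab and marker-low patients on HDI are different kinds of patients, and the treatment effect within that stratum is no longer a randomized comparison. A significant interaction may then show only that the drug acts on the marker. The stake is a reported predictive signature and cut-point that no clinician could apply at the time of decision.

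A lesser issue is that a patient has an on-treatment value only if still event-free and sampled at the draw, while RFS is counted from study entry.

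**Working it through.** **1. Can on-treatment values reach the interaction test?** Yes, by permission rather than instruction. XIX.1 allows them in the signature, XIX.2 sends the signature to the predictive test, and XIX.9 allows the risk score in.

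**2. Does treatment change the candidates?** The preliminary data in XIX.4 say so.
- Ipilimumab: circulating Treg rose by week 6 (two phenotypes, p = 0.02 and p = 0.001) and monocytic MDSC fell (p < 0.0001).
- HDI: serum VEGF fell, and IP-10 and IFN-alpha rose. All three are candidate serum proteins in XIX.2. Serum IFN-alpha at week 4 in patients receiving interferon partly reflects exposure.
- Section 1.5.3 adds: "The mean absolute lymphocyte count (ALC) increases proportionally with the ipilimumab dose".

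**3. The plan's own power.** Sample: (250 + 300) × 0.80 × 0.95 = 418. Power = Φ(√[N(log Δ)² / Σ 1/(e_ij f_ij)] − z_0.995).
- Row checked: stratum-1 frequency 0.5, hazards 1, 0.834, 0.5, 0.876.
- Δ = (1/0.5)/(0.834/0.876) = 2.101, so log Δ = 0.742.
- With exponential failure, 40 months of uniform accrual and 12 months of minimum follow-up, the event probabilities are 0.894, 0.854, 0.705 and 0.865.
- Cell fractions are 0.273, 0.273, 0.227 and 0.227, so Σ 1/(e f) = 19.73.
- √(418 × 0.742²/19.73) = 3.417; 3.417 − 2.576 = 0.841; power 0.80, as stated. All 16 rows of the table reproduce.

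The row assumes equal marker frequency by arm. If treatment moved stratum 1 to 50% on HDI and 70% on ipilimumab, power would be 0.76; at 30%/70% it would be 0.73; at 20%/80%, 0.585. These splits are assumptions.

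**4. What the test does with a treatment-altered marker.** Simulation: N = 418, two-sided α = 0.01, treatment HR 0.75, a prognostic baseline factor (log HR −0.5 per SD), no true effect modification, 500 runs. The shift and the correlation are assumptions.

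| On-treatment marker | Rejection rate | Treatment HR, marker-low |
|---|---|---|
| Unaffected by treatment | 1.4% | 0.76 |
| Mean shifted by 1 SD | 1.2% | 1.04 |
| Shifted, correlation with the factor 0.3 on ipilimumab | 25% | 0.72 |
| Correlation 0.3 only | 27% | 0.59 |

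A pure shift keeps the error rate near nominal but removes the apparent benefit in the marker-low stratum. Weakened tracking produces false interactions.

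**5. The clock.** Design model: D_HDI(t) = 0.29 + 0.71·exp(−1.423t), and D_ipi = D_HDI^0.75.
- Events by week 3: 5.6% HDI, 4.2% ipilimumab. By week 4: 7.4% and 5.6%.
- One-year RFS, all patients: 46.1% HDI, 56.0% ipilimumab.
- One-year RFS given event-free at the draw: HDI 0.461/0.926 = 49.8%; ipilimumab 0.560/0.958 = 58.4%. The gap between arms narrows from about 9.9 to 8.6 points.
- Simulated Cox fits in sampled patients gave the same marker coefficient from study entry and from a 4-week landmark (maximum difference 0.0; a true −0.5 was estimated as −0.514 both ways). Sampled patients have no events before the draw, so the risk sets at event times are identical.

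**The case against.** **Permissive wording.** The risk score only may be considered, no passage says that on-treatment values will enter the interaction test, tumor expression is measured at baseline, and the appendix's predictive evidence for ALC concerns baseline ALC. This narrows the point to circulating markers and makes ALC a weak example. It does not close the route. XIX.4 also reads one-month serum markers that worked with interferon but not under observation as a marker-treatment interaction, so the use is foreseeable.

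**Prognostic work is protected.** Single-marker models adjust for arm, and prognostic models are built within arm. That stands; the point is confined to predictive use.

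**The 25-27% rests on an assumed correlation.** True. It shows what can happen, not what to expect. The argument that a post-treatment value cannot select treatment does not depend on it.

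**Immortal-time bias.** A reader might infer that the on-treatment hazard ratios are biased because follow-up starts at entry. The documents do not support this. Bias appeared (null log HR −0.19) only when early failures without a sample were kept and coded marker-low, which the plan never proposes. Section 11.1.1 ends blood submission after the relapse sample, and Section 9.8.3 of the main plan rules out imputation.

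**Early events as a measure of bias.** A reader might take 7.4% (HDI, week 4) and 4.2% (ipilimumab, week 3), about 14% and 10% of 1-year events, as its size. They count patients outside the sampled set and compare different weeks. They are also upper values, since baseline imaging must show no disease and follow-up imaging begins near 3 months.

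**Conclusion.** The point holds for circulating markers in the predictive analyses. As written, the plan can return a predictive marker or cut-point based on values that treatment has changed and that are unavailable when treatment is chosen. Randomization supports the balance assumption only for pre-treatment markers. The size of any false signal cannot be fixed from the documents: near nominal under a pure shift, and 25-27% at a nominal 1% under the assumed loss of tracking.

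The clock is secondary. It leaves Cox marker hazard ratios among sampled patients unchanged. It does inflate 1-year RFS (by at most 3.7 points on HDI and 2.4 on ipilimumab under the design model), and this carries into the 1-year ROC curve, sensitivity and specificity.

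The co-primary RFS and OS comparisons are unaffected. The correction should be made before the marker data are analyzed.

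**What to change.** 1. In XIX.9, restrict every marker-by-treatment test, predictiveness curve and treatment-selection cut-point to pre-treatment specimens, including any risk score used there. N = 418 and power 0.80 do not change.
2. Label signatures that contain on-treatment values as prognostic only.
3. For on-treatment models, analyze only patients with the sample, say so, and measure RFS and OS from one landmark in all arms, no earlier than the latest scheduled draw (29 + 3 = day 32). Draw days count from first dose and RFS from study entry, so the text must state the landmark's origin.

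The cost is wording, plus the few sampled patients with an event between draw and landmark. Under the design model this is 1 − 0.937/0.956 = 2.0% on ipilimumab for a day-22 draw (1.4% for day 25) and 0.8% on HDI for a day-29 draw. Patients with earlier events are not an added loss, because they never had the sample.

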### **Power for Primary Objective: Prognostic Modeling**

Subjects will be divided into a training set and a validation set (250 each for the LIP and HIP groups, 300 for HDI group). Here we demonstrate our power in the development of a prognosis model in one of the ipilimumab arms. We base our power calculation on a test that compares the SN and SP simultaneously. Following the E1609 protocol, we expect that the cure rate for the ipilimumab arm will be 40% and the median RFS for the uncured patients is 0.48 years. As described above, we expect to obtain samples from  $\geq 80\%$  of the patients, after accounting for 95% assay success rate, we will have about 76 cases (patients who had event within 1 year) and 114 controls (patients who are followed up for 1 year without any event). We define a minimal useful model to be one with a sensitivity of 75% or higher and a specificity of 75% or higher. If the true sensitivity and specificity are 89% and 87% for our model, we will have over 80% power to claim that our model is significantly better than the minimal useful model ( $\alpha=0.05$ ).

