We will first use the Lasso Cox proportional hazard regression (LPHR) to develop a prognosis model for RFS using the training set. The Lasso was developed by Tibshirani 1996 and uses an  $l_1$  penalty to achieve a sparse solution, which allows simultaneous variable selection while fitting the model. This method has been applied to generalized linear regression and CoxPH models. Friedman et al. developed a fast algorithm for these methods and implemented it in a user-friendly R package, glmnet. Lasso has attracted more and more attention on the analysis of high-dimensional data because of its capability to perform the regression with outstanding accuracy in a large feature space, while simultaneously selecting the features. The tuning parameter will be trained through ten-fold (10x) cross validation within the training set. The linear combination score of the resulting model will be used to classify the patients into low-, intermediate-, and high-risk groups (cutoff at the 33% and 67% percentiles of the score). Hazard ratios (HRs) between the groups will be calculated. Log rank tests will be used to compare the RFS among these groups. The ability of this score to predict 1-year RFS will be evaluated using a time-dependent ROC curve. The area under the ROC curve (AUROC) will be calculated. An optimal cutoff point, which produces the best prediction (highest accuracy), will be chosen, and the corresponding sensitivity (SN), specificity (SP), and accuracy will be reported. The moderate number of candidate markers considered in each aim and the relatively large number of samples also enables us to use the regular CoxPH regression as a complement method to the LPHR. Markers will be evaluated for inclusion in the CoxPH model by forward stepwise selection. We will follow the same approach described above to evaluate the predictability of the model. Several popular machine-learning methods have been extended to handle right-censored data and predict subject survival status *at a specific time point*. We will use these methods as alternative methods to predict 1-year RFS for these patients and compare the performance of these methods to the LPHR model and Cox regression model. Specifically, univariate Cox regression will be used to evaluate the association of each individual marker and RFS. The BH method will be used to control the FDR at 5%. We will apply the random survival forest and the survival SVM to markers that passed the univariate analysis to generate a prognostic model to predict 1-year RFS. We will also use a bootstrap method in combination with the machine learning algorithm in marker selection. We will cross check the results of both methods for consistencies. The SN, SP, and accuracy will be calculated for each model and compared by McNemar tests between each pair of models. To avoid over fitting of the data, 10x cross validation within the training set will be used. In addition, ***the final models will be validated in the validation set.*** Specifically, the model parameters estimated using the training data will be applied to the validation set. For the survival model, the HR low-, intermediate-, and high-risk

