
groups (cutoff at the 33% and 67% percentiles of the score) will be calculated. The log rank test will be used to compare the RFS between the groups. The discrimination ability of the risk score on 1-year RFS will be assessed by time-dependent ROC analysis. *The same strategies will be used in the analysis of OS.*

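### Appendix XIX powers the biomarker primary objective on a joint sensitivity/specificity test that its validation analyses do not include, and the cutoff rule is not aligned with that test

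*Combined protocol and SAP*

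**What the plan says.** Under Power for Primary Objective: Prognostic Modeling (Appendix XIX.8):

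- "We base our power calculation on a test that compares the SN and SP simultaneously".
- "We define a minimal useful model to be one with a sensitivity of 75% or higher and a specificity of 75% or higher".
- Assuming a model that truly reaches 89% sensitivity and 87% specificity, the plan states: "we will have over 80% power to claim that our model is significantly better than the minimal useful model". This is at alpha 0.05 with about 76 cases (event within one year) and 114 controls. Sidedness is not stated, nor is the cutoff at which 89% and 87% apply.

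Under the Detailed Analysis Plan for the Primary Objective (XIX.9):

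- In development, patients are grouped at the 33% and 67% percentiles of the score. For classification, an optimal cutoff is taken, the one "which produces the best prediction (highest accuracy), will be chosen, and the corresponding sensitivity (SN), specificity (SP), and accuracy will be reported".
- Sensitivity, specificity and accuracy are compared between pairs of models by McNemar tests.
- In the validation half, the training-set parameters are applied. For the survival model the listed outputs are hazard ratios across the tertile groups, a time-dependent ROC analysis with no threshold, and a test: "The log rank test will be used to compare the RFS between the groups".

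**The concern.** The power section sets a clear standard for a useful model and sizes a test against it. The analysis section that should carry out that test does not mention the test or the 75%/75% minimum. McNemar compares one model with another, so it cannot show that either exceeds 75%/75%. The secondary predictive objective shows what is missing: there the plan reuses the same cutoff in validation, names a likelihood ratio test and fixes a significance level of 0.01.

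Two things are at stake. The quoted power attaches to no listed analysis, and whether a model has been validated is left to judgement after the data are seen. Separately, highest accuracy weights sensitivity and specificity by case share, 40:60 at the plan's counts. The powered test needs both to clear the same bar.

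**Working it through.** **Inputs.** From XIX.8: 250 patients per ipilimumab arm in the validation half, 80% with samples, 95% assay success, so 250 x 0.80 x 0.95 = 190, split 76/114. Null 75%/75%, alternative 89%/87%, alpha 0.05. Assumption: a one-sided joint test, with per-component level 1 - sqrt(0.95) = 0.0253.

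**1. The plan's own figure.** Joint power is the product of the two component powers.

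- Normal approximation with null variance: 0.884 x 0.902 = 0.798.
- Exact binomial (at least 65 of 76 and at least 95 of 114): 0.873 x 0.900 = 0.786.

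This agrees with the stated 80% to within two points. Taking alpha 0.05 for each component gives 0.872 exact; a two-sided joint test gives 0.65-0.67.

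**2. What the tertile log-rank detects.** Simulation with n = 190 and a 2-df log-rank at 0.05. RFS follows a mixture-cure model tied to a normal score by a Gaussian copula. Follow-up is either uniform over 1-4.3 years or exactly 1 year. Results at 40% one-year events:

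| AUC | SN, SP (balanced) | Log-rank significant (longer / 1-year follow-up) |
|---|---|---|
| 0.61 | 58%, 58% | 0.66 / 0.63 |
| 0.64 | 60%, 60% | 0.83 / 0.80 |
| 0.66 | 62%, 62% | 0.95 / 0.92 |
| 0.69 | 64%, 63% | 0.985 / 0.975 |

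At 45.8% one-year events the results are similar: 0.86 / 0.82 at AUC 0.64 and 0.98 / 0.98 at 0.68. With an uninformative score the rejection rate is about 5%, as it should be. The exact joint test passes every model in the table with probability below 1e-7.

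**3. The cutoff rule.** Assume, since the documents give no ROC shape, that 89%/87% is a point on an equal-variance binormal curve.

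- Separation d = 1.227 + 1.126 = 2.353, so AUC = Phi(2.353/sqrt 2) = 0.952.
- The highest-accuracy cutoff lies ln((1 - pi)/pi)/d above the midpoint d/2, where pi is the case share. At pi = 0.40 the shift is 0.405/2.353 = 0.172, so the cutoff is 1.176 + 0.172 = 1.349.
- This gives SN = Phi(2.353 - 1.349) = 84.2% and SP = Phi(1.349) = 91.1%.
- Exact joint power = 0.454 x 0.998 = 0.45.

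The case share matters, and 76 of 190 is not what the design RFS models imply:

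- XIX.8 (cure rate 40%, median 0.48 years if uncured): 0.6 x (1 - exp(-ln 2/0.48)) = 45.8%, about 87 cases.
- Section 9.4.1 (hazard ratio 0.75): 1 - (0.29 + 0.71 exp(-1.423))^0.75 = 44.0%, about 84 cases.

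| Cases/controls | Power at 89%/87% | Balanced cutoff (88%/88%) | Highest-accuracy cutoff |
|---|---|---|---|
| 76/114 | 0.79 | 0.76 | 0.45 |
| 84/106 | 0.79 | 0.80 | 0.70 |
| 87/103 | 0.74 | 0.76 | 0.69 |

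Shape matters too. At 76/114, with the case-to-control SD ratio set to 0.6, 0.8, 1.0, 1.2 and 1.5, exact power at the highest-accuracy cutoff is 0.78 (no loss), 0.62, 0.45, 0.35 and 0.29. If the cutoff is also estimated in a training set of 76/114, average power is 0.54, 0.50, 0.46 and 0.43 for ratios 0.6, 0.8, 1.0 and 1.2.

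**The case against.** Several stronger readings are tempting, and the documents do not support them.

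- **That the log-rank has replaced the joint test as the pass rule.** XIX.9 sets no pass rule. It lists the log-rank beside hazard ratios and an ROC analysis, and XIX.8 still states the 75%/75% standard. This is a gap between design and analysis, not evidence of a weaker criterion. What stands is that no criterion is stated.
- **That the highest-accuracy rule does lower the power.** The 80% is conditional on 89% and 87%. If those hold at whatever cutoff is chosen, the power is as stated. A loss requires treating them as a fixed ROC point, and its size depends on an undocumented ROC shape and on the case share.
- **That the plan's preliminary models would pass the log-rank and fall far short of the minimum.** The cross-validated AUCs quoted in XIX.4 are 72% for five-year OS in a vaccine arm and 83% for one-year RFS in an interferon arm; neither is from ipilimumab patients. Under an equal-variance binormal score, AUC 0.83 corresponds to about 75%/75%, which is the minimum itself.
- **That no cutoff can reach the validation half.** The listed outputs are introduced as those of the survival model; those of the machine-learning classifiers are not itemised. Carry-forward is unstated, not excluded.

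Highest accuracy is also a legitimate prespecified rule in itself. It is simply not matched to the test that was powered.

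**Conclusion.** The concern holds on the text for its main part: the powered joint test is absent from the validation analyses, no validation criterion is given, and nothing says that a classification cutoff is frozen for validation. The stated power reproduces, but it does not describe the analysis listed. The only hypothesis test named for the survival model is significant in roughly 80-98% of validation sets at AUC about 0.64-0.68, well below the plan's own minimum. This rests on the simulated RFS and score model.

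The cutoff part is conditional. Under equal-variance binormal scores, power falls from about 0.79 to 0.45 at 76/114, and to about 0.70 at 84-87 cases against 0.74-0.80 at 89%/87% or a balanced cutoff. There is no loss under some other ROC shapes, or if 89%/87% already applies at the chosen cutoff.

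The point is confined to the biomarker appendix; the trial's RFS and OS comparisons are unaffected.

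**What to change.** In XIX.9:

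1. Name the joint test of sensitivity above 75% and specificity above 75%, in the validation half, as the criterion for the biomarker primary objective. State its alpha and sidedness.
2. Choose the classification cutoff in the training half by a rule aligned with that test, for example maximising the smaller of sensitivity and specificity, and freeze it before the validation half is opened.
3. Label the tertile hazard ratios, log-rank and AUC as supportive.
4. State the power at that cutoff as conditional on the assumed operating point and case share, with its range.

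The cost is appendix wording and one added test on data already planned; the validation half is held out until the last stage. Raw accuracy at the chosen cutoff may be slightly lower, and fewer models will be called validated.
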